1.0 Objectives

1.1 Research Aims:

Vasomotor symptoms (VMS) affect up to 65% of breast cancer survivors and negatively impact their quality of life. VMS in African American and Latino women are significantly more severe as compared to Caucasian women. Symptom management should be a priority in Women's Health research. Few effective treatments for VMS are available. Stellate ganglion blockade (SGB) with local anesthetic, previously performed for chronic pain indications, has shown promise as a treatment for women with VMS in previous clinical trials, but has not been investigated in women with breast cancer receiving anti-estrogen therapy in a randomized, sham-control study.

We aim to evaluate the benefit of SGB in symptomatic women with breast cancer seeking relief from moderate to very severe VMS that are adversely affecting health and wellbeing.

Scope: Women with breast cancer on Tamoxifen, aromatase inhibitors or SERMs with moderate to very severe VMS will be enrolled as participants in this study.

Hypotheses:

The frequency and intensity of subjective and objective VMS will be significantly lower in women randomized to active SGB as compared to sham controls. Mood, memory, cognition, sleep, and quality of life will all be improved in the treatment group as compared to the sham-control group.

Specific Goals and Objectives:

Goal 1: To determine the effect of stellate ganglion blockade (SGB) for reducing subjective and objective VMS in women with breast cancer on tamoxifen, AIs, or SERMs

Goal 2: To evaluate the effect of SGB on mood, memory, cognition, sleep and quality of life in women with breast cancer on tamoxifen, AIs, or SERMs.

Goal 3: Using the results of this pilot study, we plan to submit an R01 grant to the National Cancer Institute for a larger scale study.

2.0 Background

Title: SGB CA Study

VMS (hot flashes and night sweats) are common in women with breast cancer in those treated with tamoxifen, aromatase inhibitors, selective estrogen receptor modulators (SERMs) and other chemotherapy¹⁻⁶. To many of these women, these symptoms are severe and intolerable, with a significant decrease in quality of life⁴. VMS are also more common in African American and Latino women³. Most importantly, VMS may be a factor in premature discontinuation of anti-estrogens therapy for women with breast cancer.

2.1 *Describe any relevant preliminary data.*

Uncontrolled studies have demonstrated improvements in the frequency and intensity of VMS following stellate ganglion blockade (SGB) with local anesthetic, with effects ranging from 45-90% reduction for 6 weeks to several months⁸⁻¹⁰. These same studies showed improvements in sleep quality as well.

The stellate ganglion is a neural structure in the anterior cervical spine region and is part of the sympathetic nervous system. It has been injected safely in the practice of pain management for more than 50 years in cases of post herpetic neuralgia (shingles), complex regional pain syndrome (CRPS) and other painful neuropathies. Prior studies have confirmed connections between the stellate ganglion and the insular cortex and hypothalamus via third order neurons.

2.2 *Describe the relevant prior experience and gaps in current knowledge*

We recently published a prospective, randomized, sham controlled study of SGB in women with natural or surgical menopause, in which we found a 52% decrease in moderate to very severe VMS in women who underwent a single SGB with bupivacaine, a local anesthetic, as compared to a 4% decrease in women in the sham control group who underwent an injection of saline¹¹. We also identified statistically significant improvements in objective hot flashes, measures of verbal learning and trends toward improved depression in the SGB treatment group, whereas such beneficial effects were not seen in the sham control group.

Only one controlled study of SGB in women with breast cancer has been published to our knowledge¹⁴. Patients with at least one month of VMS underwent either an image-guided stellate ganglion injection at the C7 level with 0.5% bupivacaine 10mL, or were prescribed pregabalin, a membrane stabilizer found to diminish vasomotor symptom in some patients, at 75 mg twice daily, and were followed for 3 months. Participants recorded the intensity and frequency of hot flashes in a diary. Both treatment groups were observed to have considerable reductions in frequency and intensity of VMS, but there was no control group in the study design and the randomization method was not described¹⁴. As it is well known that the placebo effect in hot flash studies can be dramatically high, more than 60% in some reports¹⁵, it is important to use a study design that evaluates the placebo effect of any treatment.

Title: SGB CA Study

Our prior work demonstrated a significant treatment effect with SGB for VMS. In addition to the fact that VMS are typically more severe and bothersome in breast cancer patients, VMS symptoms can be a factor in patients stopping breast cancer treatment. We feel it is important to study the effects of SGB in this patient population using a randomized sham-control study design.

2.3 Provide the scientific or scholarly background for, rationale for, and significance of the research based on the existing literature and how will it add to existing knowledge

Very few effective treatments are available for VMS, and racial and socioeconomic disparities significantly decrease access to treatments that are available. Although hormone therapy (HT) remains a highly effective treatment for VMS in some menopausal women, HT is contraindicated in breast cancer patients, breast cancer survivors, and those at risk of breast cancer or other hormone sensitive malignancies.

Non pharmacologic treatments like botanicals, acupuncture, yoga, and lifestyle interventions have shown little to no improvements in VMS symptoms in clinical trials. Although Brisdalle (Paroxetine, an anti-depressant) was recently approved by the FDA in 2013 for the treatment of VMS in menopausal women, fairly low efficacy of this therapy as compared to placebo is seen and intolerable side effects are attributed to this class of drugs (weight gain, decreased libido and anorgasmia).

The exact mechanism of SGB is not fully understood. Treatment with SGB is based on the interruption of the sympathetic nervous system, changes in blood flow and modulation of norepinephrine (NE) levels or nerve growth factor (NGF) in the thermoregulatory regions of the brain. As well, remodeling or modulation of neural receptor systems or feedback systems involving the stellate ganglion and the insular cortex, the thermoregulation and homeostatic control centers in the brain^{15, 16} are likely being affected.

In this study, we aim to assess the effects of SGB on subjective and objective VMS, mood, memory, cognition, sleep and quality of life in women with breast cancer using tamoxifen, aromatase inhibitors or SERMS in a prospective, randomized, sham-control study, with a six month follow up.

3.0 Inclusion and Exclusion Criteria

3.1 Describe how individuals will be screened for eligibility.

Patient entry, exclusion and dropout criteria:

a. General inclusion criteria include

1. aged 30 to 75 years
2. 28 or more reported moderate-to-very severe hot flashes per week
3. a minimum of two weeks of VMS diary recording prior to SGB
4. current use of tamoxifen, aromatase inhibitors, or SERMs for a breast cancer indication for at least six months

Title: SGB CA Study

5. willingness to undergo fluoroscopy-guided SGB or sham treatment.
6. if participant is on an SSRI or SNRI, they must be on a stable dose of SNRI or SSRI for previous six month
7. approval of treating psychiatrist or psychologist to participate in study if Depression and Anxiety Scale Score (DASS) score is ≥ 21 for depression or ≥ 15 for anxiety

b. General exclusion criteria include:

1. conditions that preclude SGB or sham intervention (e.g., anatomic abnormalities of the anterior neck or cervical spine; goiter, cardiac/pulmonary compromise; acute illness/infection; coagulopathy or bleeding disorder; allergic reactions/contraindications to a local anesthetic or contrast dye);
2. use of treatments in the past two months that can affect VMS (e.g., use of oral or transdermal HT or contraceptives,
3. conditions or disorders that can affect performance on cognitive tests (e.g., dementia/mild cognitive impairment; stroke; traumatic brain injury; alcohol/substance use; inability to write, speak, or read in English, English as a second language
4. Mini-Mental State Exam (MMSE) ≥ 28
5. conditions that can affect sleep quality (e.g., use of sleep agents; shift work; etc.)

3.2 *Describe the criteria that define who will be included or excluded in your final study sample.*

After participants have reviewed and signed the consent form in person, they will be interviewed to determine candidacy for the study. They will be asked to provide information about themselves and their medical history. Before the intervention procedure, they will be asked to maintain a diary of VMS. Participants will be instructed to record the frequency and severity of each hot flash or night sweat using the following definitions: “mild” (< 5 minutes, warm, red face, uncomfortable), “moderate” (< 15 minutes, warmth involving neck, ears, head, whole body, with perspiration, clammy skin, dry mouth, tense muscles, tachycardia, irritation, agitation, embarrassment), “severe” (< 20 minutes, warmth described as a raging furnace or burning up, weak, faint, headache, chest heaviness, extreme perspiration, prickling sensation over skin, heart irregularities, anxious, panic attacks) or “very severe” (< 45 minutes, boiling eruption, rolling perspiration, inability to breathe, faint/dizzy, leg/foot cramps, heart irregularities, difficulty functioning, distressed, nausea). They will be asked to do this for a minimum of two weeks prior to the procedure in order to determine eligibility for the study. VMS eligibility will be re-assessed 24 hours before the SGB. A participant will not be permitted to proceed with the initial procedure if they do not have the completed written

Title: SGB CA Study

baseline diary for a confirmatory VMS frequency and severity count at the time of the procedure.

To screen for depression, we will use the Depression Anxiety and Stress Scale (DASS). Women excluded on the basis of their DASS (≥ 21 for depression and ≥ 15 for anxiety) scores will be referred to a mental health provider.

To screen for dementia, we will administer the Mini-Mental State Exam (MMSE). Women with an abnormal or low MMSE score ($MMSE \geq 28$) will be referred to a health provider.

3.3 Indicate specifically whether you will include or exclude each of the following special populations:

The following special populations will not be included in this research:

- *Adults unable to consent*
- *Individuals who are not yet adults (infants, children, teenagers)*
- *Pregnant women*
- *Prisoners*

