9.0 Procedures Involved

9.1 Describe and explain the study design.

Title: SGB CA Study

We aim to conduct a randomized, single-site, sham-control clinical trial of SGB on VMS in 36 women with breast cancer on anti-estrogen therapy (18 per group). We will need to screen and enroll approximately 50 women to randomize 36 women. Some women may not qualify due to insufficient number of hot flashes or there may be some withdrawals. The primary entry criterion will be 28 or more moderate to very severe hot flashes per week. VMS will be measured by self-report on a written daily dairy over a 6-month period. Secondary outcomes include changes in mood, sleep, quality of life, memory performance with neurocognitive testing, and objective hot flashes measured by ambulatory monitoring (skin-conductance temperature monitoring) for 24 hours at baseline, three months and six months.

Randomization and Masking Procedures A computer-generated 1:1 block randomization scheme will be used to assign participants to receive either a SGB with bupivacaine or a sham injection with saline. Randomization will be performed by the injectionist immediately before the injection procedure by opening an opaque envelope to reveal the participant number and group assignment printed on an index card. Randomization assignment will be kept under lock and key. Participants and all other study personnel, including those who will perform follow-up evaluations, will be blinded to group assignment. The injectionist will not have access to the written VMS diaries until the conclusion of the study.

9.2 Provide a description of all research procedures being performed and when they are performed, including procedures being performed to monitor subjects for safety or minimize risks.

Screening Visit 1

Recording of Hot Flashes

After the participant has reviewed and signed the consent form, they will be interviewed to determine if they are a candidate for the study. We will ask them to provide information about themselves and their medical history. A member of the study team will administer the Depression Anxiety and Stress Scale (DASS) to ensure that participants are not suffering from extreme anxiety or depression. If they are found to have any of these conditions and meet the exclusion criterion, they will not qualify for our study and will be referred to a mental health provider.

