Individuals involved in the consent process will dialogue with the subject to insure they understand what is required. They may be asked to summarize their understanding of the goals and procedures of the study. Care will be given to ensure they do not feel like they are being "tested".

Non-English Speaking Subject-NA

Title: SGB CA Study

Waiver or Alteration of Consent Process (consent will not be obtained, required information will not be disclosed, or the research involves deception)-N/A
Subjects who are not yet adults (infants, children, teenagers) -N/A.
Cognitively Impaired Adults-N/A
Adults Unable to Consent-N/A

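### The MMSE inequality excludes and refers high scorers, although the protocol says low scorers are the ones to find

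*Combined protocol and SAP*

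**What the plan says.** Section 3.1(b) is the list of general exclusions. Item 4 reads, in full, "Mini-Mental State Exam (MMSE) ≥ 28". Item 3, just above it, excludes "conditions or disorders that can affect performance on cognitive tests (e.g., dementia/mild cognitive impairment" and other examples.

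Section 3.2 gives the reason for the test: "To screen for dementia, we will administer the Mini-Mental State Exam (MMSE"). The next sentence is the referral rule. It names the women concerned as "Women with an abnormal or low MMSE score", defines that score in brackets as MMSE at or above 28, and says they "will be referred to a health provider".

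Two other places touch on cognitive impairment. Section 3.3 lists "Adults unable to consent" among the populations not included, and Section 26.0 has the entry "Cognitively Impaired Adults-N/A". No other section gives an MMSE threshold.

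On timing, Section 9.2 names only the DASS at Screening Visit 1. The MMSE appears among the Visit 2 questionnaires, and randomization takes place at Visit 3.

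**The concern.** The rule decides who may enter and who is sent to a health provider. Its words point at low scores and its sign points at high ones, so staff cannot follow both. If the sign is copied to the screening form, women scoring 28 or more are turned away and referred as abnormal. Women with a low score and no recognised impairment, the group a dementia screen exists to find, pass item 4 and trigger no referral.

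The MMSE is also a secondary outcome in Section 8.1. No effect on that outcome, on the other cognitive measures, on the primary diary endpoint or on power is claimed, because the documents do not allow one to be shown.

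**Working it through.** There is no sample-size or power figure to reproduce. The check compares the group described in words with the group defined by the sign, and then asks whether any other section closes the gap.

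**1. Words against sign.** In Section 3.2 the clash lies within one sentence: the words select low scores and the bracket selects scores of 28 and above. Item 4 of Section 3.1(b) does not itself use the word low. It conflicts because it uses the same cut-off and sign, for a test whose stated purpose is to detect dementia. No outside knowledge of MMSE scoring is needed, since the protocol itself calls the abnormal score low.

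**2. Effect of the sign on item 4.** The printed rule is set against the two possible reversals:

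| Score | As printed (exclude ≥ 28) | Reversed, 28 admitted (exclude < 28) | Reversed, 28 excluded (exclude ≤ 28) |
|---|---|---|---|
| Below 28 | passes | excluded | excluded |
| Exactly 28 | excluded | passes | excluded |
| Above 28 | excluded | passes | passes |

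Under the first reversal the decision changes at every score. Under the second it changes at every score except 28. The referral bracket in Section 3.2 behaves in the same way.

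**3. Does another section catch the low scorer?** Item 3 concerns conditions and disorders a woman has. Section 3.3 concerns women who cannot consent. The Section 26.0 entry concerns consent procedures for impaired adults. None of them sets a rule based on a score, so none clearly picks up a woman whose impairment has not been recognised.

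**4. Number of women to whom the rule is applied.** Section 9.1 has about 50 women screened and enrolled to randomize 36. Section 21.3 has about 60 screened to randomize 30. The lower figure in each pair is the number randomized, all of whom must have passed the criteria. The upper figure is a ceiling: if the MMSE is first given at Visit 2, women who fail the telephone count of hot flashes never take it. Neither figure is a count of women misclassified. That would need a score distribution, which the documents do not give.

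**5. Can the rule be applied before randomization?** Visit 2 is 2 to 3 weeks after Visit 1, and Visit 3 is 4 to 5 weeks after Visit 1. The shortest gap is 4 − 3 = 1 week and the longest is 5 − 2 = 3 weeks. There is time, but Section 9.2 does not say that the Visit 2 score is checked against item 4.

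**6. Could the sign be a misread character?** This cannot be wholly excluded, but it is unlikely. The same sign appears in two sections, and the DASS thresholds beside it (≥ 21 and ≥ 15) read sensibly.

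**The case against.** The best reply is that the intended direction is obvious. Section 3.2 says in words that low scorers are referred, the purpose is stated, and trained staff would read the sign as a slip. It probably is one slip, copied once. But this reply accepts that the criterion is wrong as written, makes eligibility depend on staff departing from it, and leaves a score of exactly 28 undecided.

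A second reply is that item 3 does not say diagnosed or known, so a low MMSE could itself lead to exclusion under dementia or mild cognitive impairment. That reading is possible. It would still leave item 4 excluding the high scorers.

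A third concerns scope. Section 9.2 lets women who are ineligible for cognitive testing continue in the hot flash portion, and Section 12.3 makes the cognition study optional. If item 4 governs only cognitive testing, nobody is turned away from the trial on its account. This stands as a qualification: exclusion from the whole trial depends on a scope that the protocol does not state. The contradiction and the referral error do not depend on it.

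Finally, no endpoint effect is shown and the correction is very small. Both are true, and they limit how much weight the point carries. They do not justify leaving an operative threshold pointing the wrong way.

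**Conclusion.** The concern holds, with high confidence, and should be fixed. The sign contradicts the protocol's own words in the referral rule and its stated purpose in the exclusion. Used as printed, it selects the opposite group from the one described, with only a score of exactly 28 possibly unaffected. The rule is applied to between 36 and about 50 women, or 30 and about 60 on the protocol's other figures; the number misclassified is unknown.

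The conclusion assumes that the sign is printed in the protocol as it reads here. The consequence for entry to the trial also assumes that item 4 bars the whole trial and not only the cognitive testing.

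**What to change.** Reconcile Section 3.1(b), item 4, with Section 3.2 so that the direction of the inequality agrees with the description of a low score in both the exclusion and the referral rule. State how a score of exactly 28 is treated, carry the identical rule to the screening form, and state that the score is checked before randomization at Visit 3. No cut-off is proposed here; that is for the sponsor.

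Two editorial points can go into the same amendment:

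- **DASS wording.** Section 3.1(a), item 7, joins the depression and anxiety thresholds with *or* and allows entry with a treating clinician's approval. Section 3.2 joins them with *and* and speaks of women excluded, as does Section 9.2. The texts can be reconciled if excluded means failing item 7, but this should be said.
- **Scope.** State whether items 3 and 4 of Section 3.1(b) bar the whole trial or only the cognitive testing. Section 23.3 treats current substance abuse, which overlaps an example in item 3, as an exclusion from the study. That suggests a whole-trial reading of item 3 but does not settle item 4.

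The cost is a short eligibility amendment and a corrected screening form, with no extra data or patients.

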4.0 Study-Wide Number of Subjects-NA

5.0 Study-Wide Recruitment Methods-NA

6.0 Multi-Site Research-NA

7.0 Study Timelines

7.1 The duration of an individual subject's participation in the study

Subjects will participate in this research study for at least seven months. They have the option of recording hot flashes on a paper diary for an additional six months after the study ends. If they elect to do this, their participation will last at least thirteen months.

7.2 The duration anticipated to enroll all study subjects

We expect to complete enrollment within twelve months.

7.3 The estimated date for the investigators to complete this study

We expect to complete the study in approximately 1.5 to 2.0 years.

8.0 Study Endpoints

8.1 Describe the primary and secondary study endpoints.

Primary Outcome/Endpoint: reduction in frequency and intensity of VMS subjective hot flashes that have been recorded on a paper diary for the duration of the study.

Title: SGB CA Study

Secondary outcomes/endpoint: Changes in the following measures from baseline, 3 months, 6 months:

Objective hot flashes as measured over a 24-hour period with a validated skin conductance monitor

Memory: Mini-Mental State Exam (MMSE)

Mood: Depression Anxiety and Stress Scale (DASS) and Center for Epidemiological Studies-Depression (CES-D)

Cognition: Neurocognitive testing: California Verbal Learning Test (CVLT),List A, List B, List A Short-Delay Free Recall, List A Short-Delay Cued, Recall, List A Long Delay Free Recall, Long Delay Cued Recall, Card Rotation Tests, Digit Span (Forward and Backward), Benton Visual Retention Test,(BVRT), Finding As, Brief Test of Attention (BTA) Numbers, Brief Test of Attention (BTA) Letters, Logical Memory Subtest of Wechsler Memory Scale, Revised (WMS-R/LM-R), Letter, Semantic and Phonemic Fluency) Baseline and 3 months only.

QOL: Functional Assessment of Cancer Therapy-Breast (FACT-B McCoy Female Sexuality Questionnaire (MFSQ)),

Sleep: Pittsburg Sleep Quality Inventory (PSQI), Actigraphy changes in sleep Quality

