Data will be analyzed using the PROC MIXED, PROC GLIMMIX and PROC NLMIXED in SAS statistical software version 9.2. For the correlation between changes in objective VMS and changes in memory performance, we propose to examine the correlation between frequency of total objective VMS and verbal learning by conducting Pearson correlations to examine associations between changes in cognitive performance and changes in VMS. We will conduct partial correlations to examine whether these associations remained significant after controlling for changes in sleep quality (PSQI and actigraphy-based measures).

11.2 Provide a power analysis, if necessary.

A sample size of 18 in each treatment group will provide at least 80% power to test the two-way interaction between Treatment and Time with a significance level set at 0.05.

Title: SGB CA Study

We will need to screen and enroll approximately 50 women to randomize 36 women. Some women may not qualify due to insufficient number of hot flashes or there may be some withdrawals.

11.3 Describe the steps that will be taken to secure the data to maintain confidentiality (e.g., training, authorization of access, password protection, encryption, physical controls, certificates of confidentiality, and separation of identifiers and data) during storage, use, and transmission

Research files and case report forms will be stored in the research offices of [name] and will be kept in locked offices with access only to the research team. Wherever possible, subject data will be stored using only the study ID. Measures will be taken to protect all personal information and data, including keeping all data sheets under lock and key and entering data into a database that requires login identification and a password made available only to immediate study personnel. The entire study team has taken the CITI training and is familiar with confidentiality requirements and procedures.

Downloaded data from the Biolog hot flash monitor and the actigraph watch will be processed, stored, and analyzed in password-protected network at the University of Illinois in Chicago of [name]. Data related to cognitive assessments will be stored and analyzed at the University of Illinois at Chicago in [name] lab.

11.4 Describe any procedures that will be used for quality control of collected data

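### Section 8.1 names the MMSE, the trial's own entry screen, as the only memory endpoint, while Sections 9.1 and 11.1 take memory from the neurocognitive tests

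*Combined protocol and SAP*

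**What the plan says.** Section 1.1 treats memory and cognition as separate domains. Goal 2 is "To evaluate the effect of SGB on mood, memory, cognition, sleep and quality of life", and the hypothesis is that "Mood, memory, cognition, sleep, and quality of life will all be improved in the treatment group".

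Section 8.1 introduces the secondary endpoints with "Changes in the following measures from baseline, 3 months, 6 months". Under memory it lists one instrument: "Memory: Mini-Mental State Exam (MMSE". The California Verbal Learning Test (CVLT) recall scores, the Benton Visual Retention Test and the Logical Memory subtest stand under Cognition, and that battery is limited to baseline and 3 months.

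The MMSE also governs entry. Section 3.2 says "To screen for dementia, we will administer the Mini-Mental State Exam (MMSE". The exclusion list in Section 3.1 contains "Mini-Mental State Exam (MMSE) ≥ 28", and Section 3.2 attaches the same inequality to "Women with an abnormal or low MMSE score".

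Other sections take memory from different measures:
- Section 9.1 describes the memory outcome as one obtained from neurocognitive testing.
- Section 9.2 puts the MMSE among the questionnaires on mood and everyday functioning, apart from the tests of mental abilities.
- Section 11.1, for the link between objective hot flashes and memory performance, says "we propose to examine the correlation between frequency of total objective VMS and verbal learning".

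**The concern.** A report that follows Section 8.1 would answer the memory goal with the MMSE. One that follows Sections 9.1 and 11.1 would answer it with verbal learning. The plan does not choose between them. It also collects many cognitive scores and designates none of them as the memory measure, so the choice could be made after the results are seen.

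The measure that Section 8.1 does name is weak for the purpose. It is a dementia screen, and its range is restricted at entry by a cut-off on the same score. If the women admitted are those near the top of the scale, the endpoint has little upward room, and improvement is what the trial expects. A flat MMSE result could then be read as no effect on memory when it partly reflects the instrument.

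**Working it through.** **Inputs from the protocol.** 18 women per group and at least 80% power for the Treatment by Time interaction (Section 11.2); two-sided 0.05 (Section 11.1); MMSE cut-off at 28 (Sections 3.1 and 3.2).

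**Assumptions, not in the protocol.** MMSE maximum of 30; the baseline distribution over the admitted scores; the SD of change.

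**Step 1: the plan's own figure.** The 80% cannot be reproduced, because Section 11.2 gives no outcome, effect size, SD or within-subject correlation. It can be inverted for a comparison of mean change between two groups of 18:
- Normal approximation: d = (1.960 + 0.842) × √(2/18) = 2.802 × 0.333 = 0.93 SD.
- t-test: d = 0.96 SD.

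**Step 2: room to improve if women at 28 or more are admitted.** Each woman has 30 minus her entry score, so 0 to 2 points.
- Even spread over 28, 29 and 30: mean room = (2 + 1 + 0)/3 = 1.0 point, and one third start at the maximum.
- 20%, 30% and 50% at 28, 29 and 30: mean room = 0.2×2 + 0.3×1 + 0.5×0 = 0.7 point, and half start at the maximum.

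**Step 3: detectable difference against that room.** Detectable difference = 0.96 × SD of change.

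| SD of change | Detectable (points) | Share of 1.0-point gap | Share of 0.7-point gap |
|---|---|---|---|
| 0.5 | 0.48 | 48% | 69% |
| 0.75 | 0.72 | 72% | 103% |
| 1.0 | 0.96 | 96% | 137% |
| 1.5 | 1.44 | 144% | 206% |

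**Step 4: power if treatment closes half the gap, SD of change 1.0.** Power ≈ Φ(difference / (SD × √(2/18)) − 1.96).
- Even spread: Φ(0.50/0.333 − 1.96) = Φ(−0.46) = 32%.
- Half at 30: Φ(0.35/0.333 − 1.96) = Φ(−0.91) = 18%.

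**Step 5: both readings of the criterion, by simulation.** The illustration assumes a true mean of 28.5, a true SD of 1.5, a measurement error SD of 1.0, a true gain of 1.5 points and 18 per group.

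| Who is admitted | Gain seen with ceiling | Power with ceiling | Power without ceiling |
|---|---|---|---|
| 28 or more | 0.83 | 67% | 86% |
| Below 28 (as printed) | 1.40 | 87% | 88% |

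Under the printed rule every woman enters at 27 or below and has at least 3 points of room, so the ceiling costs almost nothing.

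**Step 6: which reading applies.** The exclusion in Section 3.1 removes scores of 28 and above. Section 3.2 uses the same inequality to mean an abnormal or low score. The sign and the words contradict each other. The words make entry at 28 or more the probable intention, but the documents do not settle it.

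**Step 7: what else measures memory, and when.** At 3 months the CVLT, Benton and Logical Memory tests are available. At 6 months Section 8.1 and Visit 5 in Section 9.2 omit cognitive testing, which leaves the MMSE as the only memory measure. Visit 2 in Section 9.2 says instead that cognitive testing is done at all three time points.

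**The case against.** The strongest reply is that the memory goal is not left to the MMSE. CVLT recall and Logical Memory are already secondary endpoints, Section 11.1 applies intention-to-treat mixed models to all secondary outcomes, and the correlation analysis there uses verbal learning. A benefit on verbal learning would be tested and reported under the present plan. On this view the problem at 3 months is a label. That stands: no data are lost, and a reader who infers that the trial cannot detect a memory effect goes further than the documents allow.

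Three further points against a stronger reading also stand:
- The ceiling depends on an assumed 30-point maximum and on reading the exclusion against its printed sign. The size in points also depends on assumed SDs, and the shares in Step 3 vary widely.
- A reader might infer that the MMSE can hardly change at all. Only improvement is limited; follow-up scores can fall below 28.
- Section 9.2 lets women who are ineligible for cognitive testing stay in the hot flash part, so it is unclear whether the cut-off restricts everyone with MMSE data.

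A reader might also cite Section 2.2 as treating verbal learning as memory. It reports a verbal learning benefit in the prior trial but does not call it memory; Section 11.1 is the support for that link.

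None of this makes a screening score a sound sole memory endpoint, or removes the conflict between Section 8.1 and Sections 9.1 and 11.1.

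**Conclusion.** The point holds as a defect of designation. Section 8.1 names as the only memory endpoint a measure that Sections 9.1 and 11.1 do not use for memory, and that the trial itself uses as an entry screen. This part needs no assumption.

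The ceiling is conditional. It is material if women at 28 or more are admitted and the scale ends at 30: at most 2 points of upward room each, with the detectable difference taking up about half of the average room or exceeding it, depending on the SD. It is close to nil under the criterion as printed. The claim that the MMSE could not show an effect at all is not supported, because the protocol gives no SD and no expected effect for it.

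This is a worthwhile, inexpensive correction to a secondary endpoint. It does not touch the primary outcome.

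**What to change.** - In Section 8.1, take the memory endpoint from the neurocognitive battery. Designate one CVLT score before unblinding, for example List A Long Delay Free Recall, at 3 months, with Logical Memory as support. The documents give no ground for ranking the candidate scores; what matters is that one is fixed in advance.
- Keep the MMSE for screening and description.
- Use the same CVLT score in the Section 11.1 correlation.
- Reconcile the MMSE inequality in Sections 3.1 and 3.2 with the wording that describes it, and state the scale range.
- Reconcile the cognitive testing schedule: three time points under Visit 2 in Section 9.2, against baseline and 3 months in Section 8.1 and no cognitive testing at Visit 5.

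The cost is wording only, since all these tests are already planned. There are two downsides. If the battery is not given at 6 months, the memory endpoint has no 6-month value. Sections 9.2 and 12.3 also allow women to take part without the cognitive testing, so the endpoint may rest on fewer than 36 women; the plan should say how those women are handled.
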